Due to challenges posed by the COVID-19 pandemic, social distancing practices, and aiming to create a feasible scenario to continue the current study, we propose an additional option to safely adapt study methods to deliver the study in a home-based, fully remote manner. Importantly, this scenario also presents as an opportunity to collect meaningful data on our specific aims while translating this successful research program into a remote/home-based mode of delivery. A remote/home based option may also yield valuable preliminary data that will be relevant for planning future exercise studies in aging adults in the present “new normal”.

Therefore, this research project will continue using a two-option design consisting of:

- Option A: Current, IRB-approved, in-person methods pending appropriateness based on current University of Miami recommendations and standard operating procedures as it relates to the COVID-19 pandemic.
- Option B: Remote option of current methods to maximize recruitment. This will be the only option until the study team obtains approval to resume Option A (as per University’s safety guidelines, as mentioned above).

4) Background

Individuals 65 and older will reach 30% of the global population over the next 30 years, totaling approximately 2 billion people.¹ Many will develop age-related cognitive decline, a condition for which there is no effective prevention or treatment. Therefore, the development of successful

IRB Study Number: 20180926

strategies to support cognitive health and remediate age-related cognitive decline is critically needed. Exercise is effective at improving cognitive performance,²⁻⁴ but there is considerable inter-individual variability in cognitive outcomes after exercise. A greater understanding of this variability, the mechanisms, exercise dose and type is necessary to improve the effectiveness of exercise in prevention and remediation of age-related cognitive decline.

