For Option B, we will use transcranial alternating current stimulation (tACS), which is one specific form of transcranial electrical stimulation (tES) combined with electroencephalography (EEG) to measure neuroplasticity that is similar to TMS neuroplasticity measurements. In both paradigms, the brain's response to a mild electrical stimulus is recorded. With TMS, a mild electrical stimulus is delivered with electromagnetic induction, and the response is measured with electromyography surface electrodes. With tACS, a mild electrical current is delivered with small electrodes placed on the scalp, and measured with electromyography surface electrodes. These two methods are under the same neurophysiological principles, and thus, yield comparable data.

The practical application of tACS is simple: a low intensity (1-2 mA) alternating electrical current is applied to the scalp to influence underlying cortical excitability, which is measured with non-invasive surface EEG electrodes. Direct current stimulation is presently FDA-approved for extracranial use, and FDA applications for cranial stimulation for management of mood disorder and chronic pain are in progress. The stimulator used in this study is the STARSTIM®-Home system (Neuroelectrics, Inc), a tES home-base system that recently received FDA approval for the Investigational Device Exemption supplemental protocol in a study for tES to be used to treat patients with Major Depression Disorder (MDD) due to COVID-19 related restrictions. STARSTIM®-Home system is capable of recording EEG before, during and after tACS stimulation.

Genetic factors may modify cognitive response to exercise. A common single nucleotide polymorphism of the BDNF gene (Val66Met) impairs activity-dependent release of BDNF.¹⁹ We and others have demonstrated that the Val66Met allele attenuates improvements in cognitive performance after exercise, both in young^{18,20} and old adults²¹. Furthermore, carriers of the apolipoprotein E (APOE) e4 alleles exhibit greater cognitive benefits after exercise through unknown mechanisms,^{22,23} although

IRB Study Number: 20180926

they have greater risk for AD.^{24,25} The effects of genetic factors on response to exercise will only be evaluating in the Option A.

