 - d. Any medical devices (i.e. Cardiac pacemaker, deep brain stimulator, medication infusion pump, cochlear implant, vagal nerve stimulator)
 - e. Intracranial lesion
 - f. Substance abuse or dependence within the past six months
 - g. Exclusively for Option A: TMS Neuroplasticity assessment, as per the TMS Safety Guidelines.¹³
 - i. History of fainting spells of unknown or undetermined etiology that might constitute seizures
 - ii. History of seizures, diagnosis of epilepsy, history of abnormal (epileptiform) EEG or family history of treatment resistant epilepsy

IRB Study Number: 20180926

- Pregnant women
- Vulnerable populations such as prisoners
- People unable to consent themselves
- Subjects who, in the Investigator's opinion might not be suitable for the study

[figure not shown]
6) Number of Subjects

This is not a multi-center study. We will recruit a total of 80 adults. We will use a multifaceted approach by recruiting participants from the Evelyn F. McKnight Brain Institute community memory clinic, and by advertising the study using flyers throughout the University of Miami Miller School of Medicine (UMMSM) and Coral Gables Campuses, the Miami community and participant registries. We will also recruit via online research database tool including the ResearchMatch.org. In addition, we will access University Research Informatics Data Environment (URIDE), and potential subjects will be identified and contacted via the Consent to Contact Initiative.

With a significance level of 0.05, our sample of 80 individuals will provide 80% power to detect a Cohen effect size of 0.36 using a two-sided paired t-test for Aim 1, the effect size associated with improvements in executive function in a recent meta-analysis of healthy adults 55+,²⁶ and an attrition of 20%, not uncommon in exercise intervention trials. In addition, a sample of 80 participants will provide 80% power to detect a correlation of 0.34 between the change in neuroplasticity and the change in cognitive performance.

7) Study Timelines

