- Exercise Questionnaires (literacy, self-efficacy, barriers/motivators)

Visits #4-15: Physical exercise Intervention-Moderate Intensity (estimated time per visit: 60 minutes 3 times per week for weeks 2-5, total of 4 weeks of Moderate Intensity Exercise)

- Assessment of vitals (blood pressure, heart rate)
- 60 minutes of aerobic exercise (includes 5 minute warm-up/5 minute cool-down)
- Re-assessment of vitals

Visits #16-27: Physical exercise Intervention-High Intensity (estimated time per visit: 60 minutes for weeks 6-9, total of 4 weeks of High Intensity Exercise)

- Assessment of vitals (blood pressure, heart rate)
- 60 minutes of aerobic exercise (includes 5 minute warm-up/5 minute cool-down)
- Re-assessment of vitals

Visit #28 Posttest assessment- Part 1 (estimated time: 3 hours, maybe completed on same day as Part 2, completed in week 10)

- Blood draw
- Gait and postural control assessment
- Review of the adverse effects
- TMS plasticity

IRB Study Number: 20180926

- Review adverse effects post TMS

Visit #29 Posttest assessment- Part 2 (estimated time: 1.5 hours, may be completed on same day as Part 1, completed in week 10)

- Cognitive test battery
- Exercise Testing
- Exercise Questionnaires (literacy, self-efficacy, barriers/motivators)

Optional Test visits:

- An additional testing combining TMS and EEG during pre and post testing will be offered to participants. This testing is performed to gather information about direct measure of neuronal activity. This would add approximately two hours to each visit.

Visit #4: TMS/EEG pretesting measure (estimated time: 2 hours)

- Review of adverse events
- Single pulse TMS plasticity measures
- EEG recording
- Review adverse effects post TMS

Visit #31: TMS/EEG post testing measure (estimated time: 2 hours)

- Review of adverse events
- Single pulse TMS plasticity measures
- EEG recording
- Review adverse effects post TMS

OPTION B: This option is an adaptation of the current methods that includes updating testing timeline to include a familiarization session. We updated our assessment to include outcome measures that are appropriate for remote delivery. We eliminated our genetic testing as it not possible to be performed remotely. In this option, in-person visits will be replaced with remote sessions.

Adaptations of the current timeline include:

Session #1a: Screening process:

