This is an investigator-initiated open label study in neurologically healthy sedentary adults. Participants will undergo a total of 29 or 31 sessions, including the screening session, three to four pretest (baseline) assessments, 24 aerobic exercise sessions and three to four post-test assessments. For option A, assessments will take place at the Neuromotor Plasticity Lab located at Lois Pope Life Center located at [name] and aerobic exercise visit will take place at either the UMMSM Medical Wellness Center or the UM Coral Gables Wellness Center. For option B, assessments and exercise sessions will take place in the participant home as they are monitored by a trained study member. An illustration of the experimental design is provided below:

Methods:

Subjects will participate in the Option A pending appropriateness based on current University of Miami recommendations and standard operating procedures as it relates to the COVID-19 pandemic. Given the COVID-19 pandemic, it is worth of note that potential participants may remain less enthusiastic about in-person procedures for an undetermined length of time. Thus, even in the event that the study team obtains approval to resume activities as per Option A based on University guidelines, we would like to continue to offer Option B according to participant preference. All testing procedures described for the Option A will be adapted (as feasible) for the Option B. Testing procedures that differ for the Option B are described and noted in the Option B methods.

OPTION A METHODS

TMS Plasticity

Subjects will come in for a total of 2 plasticity visits (pre and post training). We will measure plasticity in the motor cortex of the dominant hand.

Subjects will be set up in a chair with EMG electrodes placed on the first dorsal interosseus (FDI) on the dominant hand to measure motor threshold over in the corresponding (contralateral) motor cortex (M1). The motor threshold serves as the basis for the following TMS-measures over the motor cortex. When administering TMS, the figure of eight coil will be placed tangentially to the scalp with the handle pointing posterior for all stimulations. We will proceed with determining motor threshold and conduct TMS (single pulse TMS and TBS) over the dominant motor cortex. After removing the EMG equipment from the subject, a post TMS safety evaluation will be conducted.

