With a significance level of 0.05, our sample of 80 individuals will provide 80% power to detect a Cohen effect size of 0.36 using a two-sided paired t-test for **Aim 1**, the effect size associated with improvements in executive function in a recent meta-analysis of healthy adults 55+,⁴² and an attrition of 20%, not uncommon in exercise intervention trials. In addition, a sample of 80 participants will provide 80% power to detect a correlation of 0.34 between the change in TMS neuroplasticity and the change in cognitive performance for **Aim 2**, and 80% power to detect an R-Squared of 0.11 attributed to a genetic modification in the change in cognitive performance using an F-Test for **Aim 3 (Option A only)**. We expect an overall improvement in cognitive performance after aerobic exercise. Most robust improvements are expected in executive function as previously shown in elderly, but also in other cognitive domains such as processing speed and attention.¹¹

Baseline characteristics will be summarized as means \pm standard deviation or medians (interquartile ranges) for continuous variables and as frequency (%) for categorical variables. Normality for the distributions of continuous variables will be visually assessed and statistically tested. If the normality assumption is questionable, Box-Cox transformation will be used to reduce the skewness in the indicated analyses or non-parametric tests will be used. All statistical tests will be conducted against a 2-sided alternative hypothesis, employing a significance level of 0.05.

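### The 80% power stated for Aim 3 needs essentially all 80 participants to be genotyped, but only Option A participants are and Option B counts toward the same 80

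*Combined protocol and SAP*

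**What the plan says.** In section 11, Data Analysis, one sentence covers Aims 2 and 3. For Aim 2 it says that "a sample of 80 participants will provide 80% power to detect a correlation of 0.34 between the change in TMS neuroplasticity" and the change in cognition. For Aim 3, marked as Option A only, it adds "80% power to detect an R-Squared of 0.11 attributed to a genetic modification in the change in cognitive performance using an F-Test". The sentence before it, on Aim 1, assumes 20% attrition.

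The 80 is the study total. Section 6 says "We will recruit a total of 80 adults", and section 22 repeats about 80. Neither divides the number by option.

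Option B contributes nothing to Aim 3. Section 4 says "The effects of genetic factors on response to exercise will only be evaluating in the Option A", and the Option B part of section 7 says "We eliminated our genetic testing as it not possible to be performed remotely".

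Option B is also not marginal. Section 3 says of it "This will be the only option until the study team obtains approval to resume Option A". Section 9 (Methods) adds that, even after Option A resumes, "we would like to continue to offer Option B according to participant preference".

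On Aim 2, section 6 gives the same figure without mentioning TMS: "a correlation of 0.34 between the change in neuroplasticity and the change in cognitive performance". Section 11 ties it to TMS, which only Option A measures.

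**The concern.** The power sentence attaches the whole-study number to an analysis that only part of the study can enter. It was labelled for the two-option design, but its sample size was not adjusted. If the 80% already uses everyone, any Option B enrolment makes it too high.

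The consequence lies in interpretation. A null genetic result would be read against an R-squared of 0.11 detectable with 80% power, when the number genotyped may reveal only larger effects. For Aim 2, a reader cannot tell which participants the 0.34 refers to.

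**Working it through.** **Inputs from the protocol.** Two-sided alpha 0.05; Aim 3 R-squared 0.11 by F-test; 80 enrolled; 20% attrition, so 80 × 0.8 = 64 completers; Aim 1 effect size 0.36 by paired t-test; Aim 2 correlation 0.34. The numerator degrees of freedom of the genotype F-test (u) are not stated. I use u = 1 for carrier against non-carrier and u = 2 for three genotype groups.

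**Which n do the stated figures rest on?** The other two aims reproduce at 64:
- Aim 1, paired t, effect size 0.36: 81.0% at n = 64; 88.9% at n = 80.
- Aim 2, Fisher z, power = Φ(atanh(0.34) × √(n − 3) − 1.96), with atanh(0.34) = 0.354: 79.0% at n = 64; 87.4% at n = 80.

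**Aim 3.** Noncentral F with f² = 0.11/0.89 = 0.1236, λ = n × f², and degrees of freedom u and n − u − 1:
- u = 1, n = 64: λ = 7.91, power 79.1%. Matches the stated 80%.
- u = 1, n = 80: λ = 9.89, power 87.4%. Does not match.
- u = 2, n = 80: power 79.4%. Matches.
- u = 2, n = 64: power 68.9%. Does not match.

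Both matching readings use the full cohort: every completer, or every participant enrolled. The smallest n that reaches 80% is 66 at u = 1 (80.3%) and 82 at u = 2. With 20% attrition, 66 completers correspond to 66/0.8 = 82.5 enrolled.

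**If some of the 80 are in Option B.** The protocol gives no split, so the Option A numbers below 80 are assumptions. Completers are Option A enrolled × 0.8. The Aim 2 columns apply only if Aim 2 is analysed on TMS change.

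| Option A enrolled | Completers | Aim 3 power, R² 0.11, 1 df | Detectable R² at 80%, 1 df | Aim 2 power, r 0.34 | Detectable r at 80% |
|---|---|---|---|---|---|
| 80 | 64 | 79% | 0.112 | 79% | 0.344 |
| 70 | 56 | 73% | 0.127 | 73% | 0.367 |
| 60 | 48 | 66% | 0.146 | 66% | 0.395 |
| 50 | 40 | 58% | 0.171 | 58% | 0.431 |
| 40 | 32 | 49% | 0.208 | 48% | 0.478 |
| 30 | 24 | 38% | 0.264 | 37% | 0.545 |

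With three genotype groups (2 df), Aim 3 power is 69% at 64 completers, 55% at 48 and 38% at 32.

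**Aim 2 wording.** Section 6 speaks of neuroplasticity in general, and section 4 describes TMS and tACS data as comparable. On that reading all 64 completers could contribute. But section 8 defines the TMS index as a duration (time for the response to return to baseline) and the tACS index as a change in cortical excitability. They share no scale, and no rule for combining them is given.

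**The case against.** **Aim 3 is exploratory.** It is worded so throughout, and section 6 gives no power for it. This limits the consequence, but the protocol still chose to state a formal power, and that figure should fit the design.

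**The size of the loss is unknown.** Option A was the original, running study, so many of the 80 may already be in it. With 70 in Option A, power is still 73%. This stands: the lower rows of the table are illustrations, not forecasts. The mismatch itself does not depend on the split.

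**There may be slack.** Attrition is mentioned only in the Aim 1 sentence. With 1 df and all 80 analysed, 66 would suffice, leaving 14 to spare. But that reading gives 87.4%, not 80%, and 14 is fewer than the 16 expected to drop out (80 × 0.2).

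**The gap between 64 and 66 is trivial.** This is fair. The detectable R-squared at 64 is 0.112, which rounds to 0.11. The argument needs only that 64 completers is everyone, not that the study is two short.

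**A minimum for Option A may be stated elsewhere.** Part of the protocol, from section 19 up to the recruitment text, was not available to this review. No minimum appears in the rest.

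**Conclusion.** The concern holds. The arithmetic behind the 80% is sound, but it is attached to a sample that Aim 3 will not have unless essentially everyone is enrolled under Option A. The two-option design does not provide for that. At 1 df, power for R-squared 0.11 is 79% if all 64 completers are genotyped, 66% at 48 and 49% at 32, the last two under assumed splits. It is lower still if three genotype groups are compared.

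The Aim 2 part is conditional. The 0.34 has the same problem if the analysis uses TMS change as section 11 says. If TMS and tACS are to be combined, the 64-completer basis could stand, but the method of combination is missing.

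This should be fixed. It leaves the Aim 1 power calculation untouched.

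**What to change.** **Aim 3 (section 11, Data Analysis).** State the expected or actual number of Option A completers. Restate the power for R-squared 0.11, or the R-squared detectable at 80% power, at that number. State whether the genotype test has 1 df (carrier status) or 2 df (three genotypes).

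**Aim 2 (sections 6 and 11).** Make the two sections agree. Either restate the detectable correlation for Option A completers, or specify how the TMS and tACS results are combined, for example with indices standardised within option and a term for option. Keep the 64-completer basis only for a combined analysis.

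**Aim 1.** Keep 80 enrolled and 64 completers as the basis. Comparisons using tests given under only one option, such as the Stroop test or the TestMyBrain battery, will have fewer.

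The cost is wording only, with no change to design or enrolment. The stated detectable effects will become less favourable.

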Principal investigator: [name]

Protocol Title: Assessing Cognitive Improvements, Brain Neuroplasticity and the Role of Genetic Factors After Aerobic Exercise in Sedentary Adults

IRB Number: 20180926

NCT: NCT03804528

Document Version Date: 2/22/2021

IRB Study Number: 20180926

1) Protocol Title

Assessing Cognitive Improvements, Brain Neuroplasticity and the Role of Genetic Factors After Aerobic Exercise in Sedentary Adults

2) Objectives

The overall goal of the proposed study is to evaluate the effects of an 8-week aerobic exercise program on cognition and determine the relationship between cognitive improvements and neuroplasticity. Limited to Option A (See Study Options section), we will also explore the effect modification of BDNF levels and BDNF allelic status, and APOE4 status on cognitive response after exercise.

Aim 1: Quantify improvements in cognitive performance after 8 weeks (150 min per week) of moderate intensity aerobic exercise in sedentary adults ≥ 55 years of age. **H1:** We hypothesize that we will see improvements in overall cognitive performance after exercise, and greater improvements in some of the cognitive domains (e.g., in executive function and processing speed, as opposed to memory or language).

Aim 2: Determine an association between changes in plasticity, aerobic capacity, and cognitive performance overall and by cognitive domain, after 8 weeks of moderate intensity aerobic exercise in sedentary adults ≥ 55 years of age. **H2:** We hypothesize that a greater response in the brain plasticity will be associated with greater improvements in cognitive performance overall and in executive function after exercise.

Aim 3 (Option A): Explore the effect modification of BDNF (levels and Val66Met) and APOE e4 on cognitive response after exercise. **H3:** We hypothesize that individuals with greater levels of BDNF, being Val carriers or APOE e4 carriers will have greater improvement in cognitive performance after exercise.

3) Study Plan/Options

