 - The TMS-EEG integration provides real-time information on cortical reactivity and connectivity. EEG provides exquisite temporal resolution, a direct measure of neuronal activity, and is capable of differentiating inhibitory and facilitatory effects in response to TMS. Contrasting the results of TMS on EEG before and after TBS provides information about cortical plasticity (at the site of stimulation) and resulting network dynamic adaptations.
 - Brain functional connectivity and inter-regional coordination can be directly estimated from EEG's. Spontaneously occurring potentials across EEG channels will be detected prior and following stimulation using already developed event detection algorithms. Measurements following single-pulse TMS provide insights on cortical excitability. The EEG cap will be placed at the beginning of the session and will remain on for the duration of the visit.
- **tACS/EEG Plasticity**
 - An index of change in the tACS-induced modulation of cortical excitability will be defined for each participant. Brain functional connectivity and inter-regional coordination can be directly estimated from EEG's. Spontaneously occurring potentials across EEG channels will be detected prior to and following stimulation using already developed event detection algorithms.

Cognitive performance

- Cognitive performance will be assessed using a neuropsychological test battery. Executive function will be assessed using the Digit Span subtest of the Wechsler Adult Intelligence Scale – Fourth³⁰, processing speed will be assessed using the Trail-Making Test Part B³¹ and the Stroop color-word test²⁹, global cognition will be assessed with the repeatable neuropsychological battery (RBANS)³⁰; and the Delis-Kaplan Executive Function System (DKEFS)³¹ will test for language.

IRB Study Number: 20180926

- Option B: the same cognitive battery, except for the Stroop color-word test, and with the addition of a TestMyBrain.org³² battery of Digit Symbol Matching, Simple and Choice Reaction Time, and Gradual Onset Continuous Performance Test will be used via a secured Zoom Platform.

Gait and postural control

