In the univariate analysis, we will compare the cognitive performance (overall and by domain) before and after exercise, using paired t-test to test for **Specific Aim 1**. For **Specific Aim 2**, we will examine the relationship between the change in TMS neuroplasticity and the change in cognitive performance using Pearson product-moment correlation coefficient. For **Specific Aim 3**, we will compare mean change in cognitive performance across subgroups by genotype using F- test. In the multivariable analyses, we will adjust for baseline characteristics (age, sex, race- ethnicity, education) using mixed effect modeling to quantify improvements in cognitive performance after exercise (**Specific Aim 1**), and to determine an association between changes in TMS plasticity, cognitive performance and changes in aerobic capacity (**Specific Aim 2**). We will use modification models by including interaction terms (time-by-genotype) to explore the relationship between change in cognitive performance after exercise and BDNF levels, Val66Met, and APOE e4 status (**Specific Aim 3-Option A only**).

12) Provisions to Monitor the Data to Ensure the Safety of Subjects*

Monitoring the safety of participants with respect to TMS neuroplasticity assessment

TMS has been used in a growing number of laboratories worldwide since 1984. A series of adverse events have been identified since then, and have been thoroughly reviewed for the development of recommended safety guidelines and precautions for the use of TMS, first at a consensus conference at the NIH in June, 1996 and, more recently, in 2008 in Siena (Italy), in a

IRB Study Number: 20180926

meeting of an international panel of TMS experts ([The Safety of TMS Consensus Group](#)).

The principal investigator will ensure that these guidelines are well-known by all study investigators and will carefully follow these updated safety guidelines in the present study. Additionally, we will track and report any adverse events that may occur.

Monitoring the safety of participants with respect to tACS neuroplasticity assessment

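### Aim 1 tests cognition overall and by domain, each at 0.05, with no primary outcome and no multiplicity control, and the 80% power belongs to no named score

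*Combined protocol and SAP*

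**What the plan says.** Section 11 (Data Analysis) sets a single rule for all aims: "All statistical tests will be conducted against a 2-sided alternative hypothesis, employing a significance level of 0.05". For Aim 1 it adds that "we will compare the cognitive performance (overall and by domain) before and after exercise, using paired t-test", and then repeats the comparison in a mixed model adjusted for age, sex, race-ethnicity and education. If normality is doubtful, a Box-Cox transformation or a non-parametric test may replace the planned one.

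H1 in section 2 reads: "We hypothesize that we will see improvements in overall cognitive performance after exercise, and greater improvements in some of the cognitive domains". Executive function and processing speed are its examples of larger gains; memory and language are the contrast.

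The power statement, given in sections 6 and 11, starts from "our sample of 80 individuals", allows for "an attrition of 20%, not uncommon in exercise intervention trials", and claims "80% power to detect a Cohen effect size of 0.36 using a two-sided paired t-test for" Aim 1. The 0.36 is described as "the effect size associated with improvements in executive function in a recent meta-analysis of healthy adults 55" and over.

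Section 8 lists the cognitive battery (Digit Span, Trail Making Part B, Stroop, RBANS, D-KEFS) without making any score primary. It assigns global cognition to the RBANS, but section 11 does not say that overall performance means the RBANS total. Option B omits Stroop and adds four TestMyBrain tests. Aim 3 is described throughout as something to explore.

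**The concern.** The 0.05 level is set for each test, while the Aim 1 question, whether cognition improved, is put to several scores at once. With no score named in advance and no adjustment, the chance that at least one score reaches significance by luck exceeds the stated level.

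The plan also leaves open which score stands for which domain. Section 8 files Digit Span under executive function; section 9 describes it as attention and working memory. Section 8 files Stroop under processing speed; section 9 describes it as response inhibition, mental flexibility and attentional control. Trail Making Part B is processing speed in section 8, and section 9 adds task switching. After the data are seen, more than one score could be presented as executive function or as overall cognition, each by more than one analysis.

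The power sentence does not settle the matter. Its effect size is for executive function, the hypothesis puts overall cognition first, and neither is tied to a score. Section 4 says the data are meant to support a later grant application, so a chance finding could be carried forward.

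**Working it through.** **Inputs from the documents.** 80 enrolled and 20% attrition, so 80 × 0.8 = 64 completers; d = 0.36; two-sided 0.05; paired t-test (sections 6 and 11).

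**Step 1: the plan's own figure.** Power is P(|T| > t(0.975, 63)), where T is noncentral t with 63 degrees of freedom and noncentrality d√n = 0.36 × 8 = 2.88. This gives 80.9%. The smallest n that reaches 80% is 63. The stated 80% is therefore reproduced for one unadjusted test.

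**Step 2: inputs that the documents do not give.** The number of Aim 1 tests (k) and the correlation between them (ρ) are assumptions.
- k = 4: the four constructs in section 8 (executive function, processing speed, global cognition, language).
- k = 10: RBANS total, the five RBANS domains, Digit Span, Trail Making Part B, Stroop and D-KEFS.
- ρ from 0 to 0.7, the same for every pair.

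**Step 3: chance of at least one false result when nothing has changed.** A two-sided 0.05 test has 0.025 on the improvement side.
- Independent tests, either direction: 1 − 0.95^k. For k = 4, 18.5%; for k = 10, 40.1%.
- Independent tests, improvement only: 1 − 0.975^k. For k = 4, 9.6%; for k = 10, 22.4%.
- Correlated tests: write each test statistic as √ρ·U + √(1−ρ)·e, with U and e standard normal, and average over U the probability that no statistic passes 1.96.

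| k | ρ | Any false significant result | False improvement |
|---|---|---|---|
| 1 | – | 5% | 2.5% |
| 4 | 0 | 18.5% | 9.6% |
| 4 | 0.5 | 15.6% | 7.8% |
| 4 | 0.7 | 13.0% | 6.5% |
| 10 | 0 | 40.1% | 22.4% |
| 10 | 0.5 | 28.7% | 14.4% |
| 10 | 0.7 | 21.3% | 10.7% |

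False improvement is thus 6.5 / 2.5 = 2.6 to 22.4 / 2.5 = 9.0 times the single-test rate. The ten-test row at ρ = 0 is an outer limit for that count, because RBANS total contains its own five domains and cannot be independent of them.

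The adjusted mixed model is not counted as a further set of tests. With complete pairs, covariates fixed over time and entered as main effects leave the estimated change the same. With attrition the two analyses can differ, so the plan has a choice of p-value rather than a doubled family.

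**Step 4: what adjustment over all scores would cost.** At 64 completers and d = 0.36, power at the first Holm step is 62.2% for four tests (0.05/4) and 49.3% for ten (0.05/10). The effect detectable with 80% power rises from 0.36 to 0.43 or 0.47. A primary score tested alone at 0.05 avoids this loss.

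**The case against.** The best defence is that this is an open-label study with no control group described, meant to gather data for a later application, and that it states a specific hypothesis. H1 predicts an overall gain with larger gains in named domains. No rule in the plan says that one significant score is enough to declare improvement, and Aim 3 is already exploratory. The 80% power is correct for each unadjusted paired test.

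All of that stands, and it rules out several stronger readings that a reader might infer.
- **That a false improvement has a 15% to 41% chance.** Figures of that size describe a significant result in either direction. The improvement side is about half as large; 41% would need about 21 independent tests.
- **That all three aims form one family of 24 tests** (four scores × (1 + 2 + 3)). Section 11 does not support this count. Univariate Aim 2 uses only the correlation with plasticity, and univariate Aim 3 only the genotype comparisons; aerobic capacity and BDNF level enter the models alone. Aim 3 is also exploratory.
- **That any single significant score would establish the claim.** The documents state no such rule.
- **That the power figure is wrong.** It is right for one test; what it lacks is a named outcome.

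The defence does not remove the gap. H1 leads with overall cognition, yet section 11 neither ties it to a score nor sets an order of testing.

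**Conclusion.** The concern holds for Aim 1 and, to a lesser degree, for Aim 2, which relates overall and domain scores to plasticity and aerobic capacity under the same rule. With an assumed 4 to 10 Aim 1 tests and correlations of 0.7 to 0, the chance of any false significant result is about 13% to 40%, and of a false improvement about 6.5% to 22%. These ranges rest on the assumed count and correlation; that the plan fixes neither is part of the fault. The power sentence is arithmetically sound for one test but is not linked to a primary score. Lack of adjustment in Aim 3 is minor if the results are reported as exploratory. I class this as a cheap improvement.

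**What to change.** Amend section 11, and the matching power sentence in section 6, before outcome data are examined.

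1. Name one primary Aim 1 score collected in both options, which excludes Stroop, and one analysis for it at two-sided 0.05. Label the other analysis supportive.
2. Make the power sentence match. Either choose an executive-function score collected in both options, to which d = 0.36 applies (settling first how sections 8 and 9 classify it), or choose RBANS total and state 0.36 as the detectable effect. The meta-analysis figure should not simply be moved to RBANS total: its five domains include no executive one, and H1 expects smaller gains in memory and language.
3. Test the remaining overall and domain scores as secondary under Holm within Aim 1, and list them so that the count is fixed.
4. For Aim 2, name one primary pair, change in plasticity with change in the same score, and put the other pairs under Holm.
5. Report Aim 3 as exploratory, as the plan already describes it.

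The cost is about a paragraph and one edited sentence. Secondary domain results will need smaller p-values. No more participants are needed, because the primary test stays at 0.05.
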